3.4. Diagnosis

The patient's dental and medical history, demographic data (age, gender) are recorded and a thorough clinical examination, as well as radiological examination, is performed. During clinical examination, the relevant tooth, and surrounding tissues, as well as adjacent lymph nodes, are examined. Percussion and palpation tests, and periodontal probing of the relevant tooth are performed. A cold test (Roeko Endo-Frost, Coltène/Whaledent Langenau, Germany) is used to assess sensitivity. Periapical radiographs (KODAK RVG 5100, Carestream Health, Rochester, NY, USA) are produced with a paralleling technique for evaluation of periradicular tissues (exposure time: 0.16 s, exposure dose: 1.22 mGy). All findings of patients will be recorded in patients' charts.

After being trained by a blinded investigator, all participants will be asked to grade their pain intensity level on a horizontal Visual Analogue Scale (VAS) before the treatment procedure. This scale is a horizontal 100 mm bar, marked in every 10mm with two ends. One end (0) indicated "no pain" and the other end (10) indicated "worst pain possible". Categorization of pain scores is as follows: 0-4 mm = No Pain, 5-44 mm = Mild Pain, 45-74 mm = Moderate Pain, 75-100 mm = severe pain. After grading the pain level, the distance between the marked point and the "no pain" endpoint will be measured with a ruler to calculate the pain intensity level. Clinical and radiological findings consistent with the asymptomatic tooth with nonvital pulp tissue with the preoperative pain intensity scores in the category of "no pain" will be included in the study. (**Eyüboğlu & Kim 2020**).

3.5. Randomization and Blinding

The patients will be randomly assigned to one of the two groups based on the irrigation protocol (Group 1-named "CONI" (conventional irrigation), and Group 2- named "INCA" (inertial cavitation)). To rule out the potential influence of the tooth type (molar, nonmolar) on postoperative pain, stratified randomization will be performed (**Nagendrababu & Gutmann 2017**). Blocks with different sizes of 2, 4 and 6 and an allocation ratio of 1:1 will be prepared (<https://www.randomizer.org>).

All allocations containing the unique randomization number and group name (CONI or INCA) will be concealed in opaque sealed envelopes which will be marked with the abbreviations "M" (molar) and "NM" (non-molar).

Due to the nature of the study, both patient and the operator could not be blinded to the treatment protocol. However, the data collector will be blinded to the objectives and the design of the study.

4. Patient information and informed consent to participate:

All patients participating in the study have to be informed in oral form by the Investigator. Additionally, patients will receive an information form, on which they shall give their written consent to participate in the investigation. This form will be countersigned by the Investigator and the Patient.

5. Confidentiality:

Data will be collected with a browser-based electronic data capture system. No personal data such as name, address, date of birth will be collected with this system. The data will be accessible to the sponsor within this system. The identification codes, used by the "Investigator" to put the results of the study in a certain relation, have to be kept confidential by the Investigator after completion of the study.

6. Clinical Procedures

6.1. Endodontic procedures

All treatment procedures will be performed in a single visit by a single treatment provider. It will be assured that the operation room is quiet and isolated throughout the whole process to avoid any outside interference. Patients will be made comfortable and informed about the steps of the procedure a second time right before commencing the treatment protocol. Patients will be also reminded that they will get the necessary treatment even if they decline from the study and should not feel compelled to participate the study for a proper treatment. All root canal treatments will be performed using a dental loupe with a magnification of 4.50X (EyeMag Pro F; Carl Zeiss).

Each tooth will be anaesthetized with 2 mL local anaesthetic solution containing 40 mg/mL articaine hydrochloride and 12 mg/mL epinephrine hydrochloride (Ultracaine DS Forte; Aventis Pharma). After isolating the tooth with a rubber dam (Hygenic Dental Dam Kit; Coltene/Whaledent GmbH & Co.kg, Langenau, Germany) the operation field will be disinfected using 5.25% NaOCl solution (Wizard; Rehber Chemistry) soaked cotton rolls.

After the access cavity preparation, a #10 C-File (MMC file, Coltene-Micro-Méga, Besançon, France) will be introduced into the root canal for scouting. Coronal flaring of root canals will be performed using a nickel-titanium flaring file (One Flare; Coltene-Micro-Méga) with an electric endodontic motor (Dual Move, Coltene-Micromega). Working length determination will be performed with a #10 C-file (MMC file, Coltene-Micro-Méga) and glidepath preparation will be completed with a One G (Coltene-Micro-Méga). The shaping of the root canals will be performed using One Curve (#25/0.06, Coltene-Micro-Méga). If further shaping of the canal will be needed 2 Shape F35 (#35/0.06) (Coltene-Micro-Méga) files will be used according to apical canal lumen. All rotary files will be used according

to the manufacturer's instructions. The filing protocols and files used will be recorded in the patient file.

In Group 1, 2 mL of NaOCl solution will be used after each file as an irrigation solution. After the shaping of the root canal is completed final irrigation with a 31G double side vented tip is performed in each canal using 2.5 mL of 5% EDTA (Wizard; Rehber Chemistry) for 1 minute, 2.5 mL of 5.25% NaOCl for 30 seconds and 5 mL of saline solution for 30 seconds respectively.

In Group 2, 2 mL of NaOCl solution will be used after each file as an irrigation solution. After the shaping of the root canal is completed, the NaOCl solution is removed from the root canal with 2.5 mL saline solution using a syringe with a 31G needle. EndoClean tip is introduced into the root canal, always maintaining a distance of at least 3mm from the apex. The EndoClean device is used for 60 seconds for each root canal.

In both groups, following root canal preparation, a matching gutta-percha cone (#25/0.06 or #35/0.06) (MM GP Points, Coltene-Micro-Méga) is introduced into the root canal coated with a calcium silicate-based root canal sealer (BioRoot RCS; Lancaster PA, USA). Single-cone technique is used to fill the root canals.

Total-etch technique is used to restore the coronal part of each tooth. The cavities are etched with 35% H3PO4 for 15 seconds before a single layer application of an adhesive material (Adper Single Bond 2; 3M ESPE). After photopolymerization (Elipar S10, 3M ESPE) of the adhesive material for 20 seconds, a flowable bulk-fill composite material (Estelite, BulkFill Flow, Tokuyama Dental, Tokyo, Japan) is used to restore the coronal cavity incrementally with a thickness of 4 mm for every layer. Each layer is photopolymerized for 20 seconds.

6.2. Post-endodontic pain assessment

After the treatment, all participants will be provided with analgesics (75 mg diclofenac sodium) (Voltaren SR 75 mg, Novartis, Kurtköy, İstanbul) and will be advised to use them if needs be and record the time of use. A pain intensity evaluation diary including VAS diagrams with their respective follow-up evaluation times will be provided to each participant to mark their pain. All participants will be contacted on their follow-up time to remind them to mark their pain intensity scores. Pain intensity of patients will be evaluated at 6h, 24h, 48h, 72h and 1 week after the completion of root canal treatment as previously described. Any complication such as paraesthesia, acute exacerbations, flare-ups, swellings will be also recorded on patients' charts. Patients who fail to abide by the follow-up time will be traced via phone, e-mail or SMS to determine the possible reasons for dropout.

7. Concomitant Treatments

Medications given to patients are to be documented

8. Schedule

The duration of the investigation and the post-assessment has to be justified.

Study duration:

Step 1. Patients enrollement: 2 months

Step 2. Treatment duration: 1 visit to dentist

Step 3. Follow-up period: 1 week

Flow chart of the study:

Investigation Periods	Consent (ICF) Screening	Treatment	Follow-up				
Visit	1 On-site	2 On-site	3	4	5	6	7 On-site
Time (hour, day, week)	-1 week	0	6 hours	24 hours	48 hours	72 hours	1 week
Patient consent (ICF)	x						
Demographics	x						
Medical History	x						
In- /Exclusion Criteria	x	x					
Dental Examination	x						x
X-ray		x					
Randomization		x					
Medical device application		x					
Concomitant Therapy,	x	x	x	x	x	x	x
(Serious) Adverse Events, Adverse device effects	x	x	x	x	x	x	x
Pain intensity			x	x	x	x	x
Pain intensity diary dispensing		x					
Pain intensity diary collection							x

9. Reporting of Unexpected Serious Adverse Events, Serious Adverse Events and Adverse Events

Unexpected Serious Adverse Events and Serious Adverse Events must be reported to the sponsor within 24 hours after awareness of the event by the Investigator. Unexpected Serious Adverse Events must be reported to the Ethics Committee and Regulatory Authority within identified timeline as per the regulations.

10. Premature Termination of the Study

If excessive pain will be experienced by three concomitant patients the study will be terminated.

11. Statistical Analysis

Statistical analysis will be defined on later stage. It is a pilot study with exploratory statistics.

12. Financing and Insurance

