3.3.1.1. Sample Size Calculation

In order to determine the number of samples, power analysis was performed using the G*Power (v3.1.9.2) program. The power of the study is expressed as $1-\beta$ (β = probability of type II error). Based on the postoperative 6th-hour pain measurements in the article by D. Liapis et al.*, the mean for

Group I was 13.9 SD:16.2; When the mean for Group II was taken as 4.9 SD: 7.3, the effect size (d) was found to be 0.716 in the calculation made to obtain 90% power at the $\alpha=0.05$ level. Accordingly, it was calculated that there should be at least 42 people in each group and 84 people in total. Considering that there may be losses during the study process (20%), it was decided to take at least 50 people in each group.

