3.3.1.2. Pilot Study

10 patients will be involved in a pilot study. There will be 5 patients in each group: manual final irrigation and EndoClean device. Pilot study will be conducted for two reasons. The first reason is to ensure the safety of the device for clinical use. Thesecond reason is to conduct an accurate power analysis and therefore, a sample group for the full clinical study. A full clinical investigation will be performed once the pilot study is done, and which will be powered according to the outcome of the pilot study.

3.3.1.3. Inclusion Criteria:

1. Physical status classification system described was used for patients' recruitment. Healthy patients, who were classified by the American Society of Anaesthesiologists (ASA) as ASA I and II
2. Patients with the age of 18 and over
3. Patients who were diagnosed as in need of non-surgical orthograde root canal treatment of an asymptomatic tooth
4. Tooth without signs of previously initiated Root Canal Therapy

3.3.1.4. Exclusion Criteria:

1. Pregnant and lactating females
2. Patients with chronic periodontal diseases
3. Patients with sensitivity or adverse reactions to any medication or materials that were used throughout the treatment procedure
4. Patients with acute periapical periodontitis
5. Patients with acute periodontal abscess
6. Patients who could not abide by the follow-up time
7. Patients who used analgesics 1-week prior or antibiotics 1-month prior to treatment
8. Uncooperative patients
9. Teeth that cannot be made functional nor restored or difficult to access teeth with no importance (wisdom teeth)
10. Teeth with poor prognosis, for example, due to deep root caries or big root resorption
11. Teeth with ≥ 4 mm periodontal pocket depth
12. Teeth with an inaccessible root end
13. Teeth with apical resorption or a radiologically not clearly defined apex
14. Fractured teeth
15. Teeth with immature or open apices
16. Teeth with root apices extending into the maxillary sinus

17. Teeth with external resorption communicating with the pulp

3.3.1.5. Withdrawal Criteria:

Subjects may be withdrawn from the study at the discretion of the Investigator or Sponsor due to a safety concern or if judged non-compliant with trial procedures.

A subject must be withdrawn from treatment if one of the following applies:

- Subject chooses to withdraw from the study at any time;
- Intolerable adverse effects;

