4.1 Primary Outcome: All participants will be asked to grade their pain intensity level on a horizontal Visual Analogue Scale (VAS) before the treatment procedure. This scale is a horizontal 100 mm bar, marked in every 10mm with two ends. One end (0) indicated “no pain” and the other end (10) indicated “worst pain possible”. Categorization of pain scores is as follows: 0-4 mm = No Pain, 5-44 mm = Mild Pain, 45-74 mm = Moderate Pain, 75-100 mm = severe pain. After grading the pain level, the distance between the marked point and the “no pain” endpoint will be measured with a ruler to calculate the pain intensity level. Clinical and radiological findings consistent with the asymptomatic tooth with nonvital pulp tissue with the preoperative pain intensity scores in the category of “no pain” will be included in the study.

4.2 Secondary Outcome: If excessive pain will be experienced by three concomitant patients the study will be terminated.

5. Populations to be Analysed

Data of all randomised study subjects will be analysed. This will be seen as the primary population for the analysis. For any specific analysis, study subjects with missing data on any of the variables in the model will be excluded from the analysis.

6. Analyses

All outcomes will be presented using descriptive statistics; normally distributed data by the mean and standard deviation (SD) and skewed distributions by the median and interquartile range (IQR). Binary and categorical variables will be presented using counts and percentages. Python programming language and its dependent statical libraries will be used for all statistical analysis.

The subsections below will describe analyses in addition to the descriptive statistics.

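### A patient who misses the week-1 visit can lose every pain score already marked: tracing asks only for reasons, and SAP section 5 drops incomplete subjects

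*Protocol*

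**What the plan says.** Protocol 6.2 gives each patient a diary with VAS lines for 6, 24, 48 and 72 hours and 1 week. Patients are contacted at each time, and the stated purpose is to remind them to mark the line. Protocol 3.4 describes how a score is obtained: the mark's distance from the no-pain end is measured with a ruler.

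In the section 8 flow chart the row "Pain intensity diary collection" is ticked once, at visit 7 (1 week, on site). The rows for pain intensity, adverse events and concomitant therapy are ticked at every follow-up point.

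On patients who do not keep to follow-up, Protocol 6.2 says: "Patients who fail to abide by the follow-up time will be traced via phone, e-mail or SMS to determine the possible reasons for dropout". It does not mention asking for the diary, the scores, the analgesic times or complications.

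SAP section 5 opens with "Data of all randomised study subjects will be analysed". It then adds that, for any given analysis, a subject lacking data on any model variable is left out. SAP 6.1 plans a model of pain over the five times, with subject as a random effect and treatment and visit as fixed effects.

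Protocol 3.3.1.1 allows 20% for losses and enrols at least 50 per group.

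**The concern.** A patient may mark four of the five lines on time and then not attend at 1 week. The scores exist on paper, and the site is already trying to reach that patient. Followed as written, the plan asks why the patient left and does not ask for the diary.

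The stake is mainly bias. Patients know their treatment (Protocol 3.5) and the outcome is self-reported pain, so attendance at 1 week may depend on pain or on care sought elsewhere. A mixed model can use a partial set of scores, but it can do nothing for a patient who contributes none. The subject-level exclusion in SAP section 5 would also remove patients whose diaries are only partly filled in.

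In the pilot, with 5 patients per arm, one lost diary is 1/5 = 20% of an arm. The pilot's scores are meant to set the size of the full study.

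**Working it through.** **Inputs.** Protocol 3.3.1.1 gives the 6-hour planning values: "Group I was 13.9 SD:16.2; When the mean for Group II was taken as 4.9 SD: 7.3". It also states that "the effect size (d) was found to be 0.716 in the calculation made to obtain 90% power", at alpha 0.05, with 42 per group needed, a 20% loss allowance and at least 50 per group enrolled. Allocation is 1:1 (Protocol 3.5). Sidedness is not stated. Two-sided is inferred because it reproduces the 42.

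**Step 1: the plan's own figure.**
- Difference = 13.9 − 4.9 = 9.0 mm.
- Common SD = √[(16.2² + 7.3²)/2] = √157.865 = 12.56 mm.
- d = 9.0/12.56 = 0.716.
- Two-sided two-sample t test (noncentral t): power is 89.3% at 41 per group and 90.04% at 42. The stated 42 is reproduced.

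**Step 2: power after loss and recovery, with 50 enrolled per group.** The documents do not say how many lost patients hold a marked diary, so this is a range.

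| Situation | Analysable per arm | Power |
|---|---|---|
| 20% lost, none recovered | 50 × 0.80 = 40 | 88.6% |
| 20% lost, half recovered | 50 × 0.90 = 45 | 91.9% |
| None lost, or all recovered | 50 | 94.4% |

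The worst row is 90 − 88.6 = 1.4 points below target. The full span is 94.4 − 88.6 = 5.8 points. Two limits apply. These figures are for the 6-hour t test, not for the SAP 6.1 model. They also count every recovered diary as an analysable patient, which SAP section 5 would prevent for a diary without a week-1 score.

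**Step 3: bias (assumed inputs).** Suppose a fraction L of an arm is lost and those patients average k mm more pain than the patients who stay in that arm. The arm's full mean then exceeds its observed mean by L × k. With the same k in both arms, the observed difference shifts by (L₁ − L₂) × k. With losses of 30% and 10%, which average the planned 20%:

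| Assumed excess k | Shift = 0.20 × k | Share of 9 mm |
|---|---|---|
| 5 mm | 1 mm | 11% |
| 10 mm | 2 mm | 22% |
| 20 mm | 4 mm | 44% |

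The arm with more loss looks less painful than it is. With equal loss and equal excess, the shift is (0.20 − 0.20) × k = 0.

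**The case against.** The strongest case against is that the plan already limits the loss. Follow-up lasts one week and everyone is contacted at each time point. Adverse events and concomitant therapy are ticked at all seven visits, the power cost is small, and Protocol section 11 calls the study an exploratory pilot. Most of this stands, and it rules out several stronger readings.

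- A reader might infer that complications are lost as well. The flow chart does not support that. A patient who misses only week 1 has four earlier follow-up points at which events are scheduled to be recorded. The gap covers events after the last successful contact.
- A reader might link exclusion 6, "Patients who could not abide by the follow-up time", to the similarly worded tracing sentence and conclude that dropouts are removed after randomisation. It is an eligibility item, eligibility is ticked only at screening and treatment, and SAP section 5 starts from all randomised subjects. No text removes a randomised patient under it.
- A reader might take 20% as the share of scores lost. It is a planning allowance for all losses, including withdrawals and patients who never marked a line. It is neither a ceiling nor the recoverable share.
- A reader might say that the protocol discards data. It does not; it fails to ask for them. The dropping comes from the SAP's missing-data rule.

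The reminders do not close the gap for pain scores. The pain ticks at 6 to 72 hours fit the patient marking the diary, no text has staff take the score then, and a ruler measurement needs the page.

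**Conclusion.** The point holds in a limited form. The documents establish that the only described source of the VAS scores is handed in at a single visit, that tracing has one stated purpose, and that a literal reading of SAP section 5 excludes subjects with incomplete data. Together these let scores that were properly marked go unanalysed.

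The effect on power is minor: 88.6% to 94.4% for the 6-hour comparison across the range from full allowance lost to nothing lost. The possible bias is 1 to 4 mm against 9 mm, but only under an assumed loss imbalance of 30% against 10% and an assumed 5 to 20 mm excess among lost patients. It is zero if loss and excess are balanced. Neither range is a forecast, because the documents give no loss by arm and no pain level among those lost. This is a worthwhile, inexpensive improvement to make before enrolment, not a flaw that undermines the design.

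**What to change.** Make two changes together; the first is incomplete without the second.

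1. **Protocol 6.2.** State that at the tracing contact the site also asks for the marked diary (by post, or a photograph of each page), and records analgesic use and any complications since the last successful contact. Scores marked at the scheduled time are analysed; scores recalled at the contact are listed separately.
2. **SAP section 5.** Replace the subject-level exclusion with use of all available scores in the mixed model of SAP 6.1, so that a partial diary contributes the times it covers.

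Optionally, add to Protocol 3.3.1.4 that exclusion 6 applies before randomisation only. This is a clarification, not the correction of an error.

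The cost is a few sentences and some extra questions in a contact already planned. The downside is that a line measured from a photograph is slightly less precise than one measured on the original; the 10 mm marks on the scale allow rescaling.

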12.1. Reimbursement of Patients' Expenses

The Sponsor shall provide the materials used for the patients.

Statistical Analysis Plan (SAP)

Comparative evaluation of the effectiveness of root canal preparation after irrigation using endodontic needle and inertial cavitation: A randomized controlled trial

Sponsor: Lumendo AG,
[name]

ClinicalTrials.gov identifier: NCT05374434

Author: [name], MS
Statistician, Data Scientist

1. Introduction	3
2. Study Design.....	3
2.1. Sample Size Calculation	3
3. Objectives.....	3
4. Outcomes.....	4
4.1 Primary Outcome:.....	4
4.2 Secondary Outcome:.....	4
5. Populations to be Analysed	4
6. Analyses	4
6.1 Outcome	4

1. Introduction

The primary objective of this randomized controlled trial is to compare the postoperative pain intensity levels in patients with asymptomatic teeth diagnosed for non-surgical orthograde root canal treatment that are disinfected during the root canal treatment procedure by manual irrigation with sodium hypochlorite (NaOCl) solution or EndoClean. The null hypothesis is that there will not be a significant difference in postoperative pain intensity levels between patients who will undergo root canal treatment with manual irrigation with NaOCl or EndoClean.

This statistical analysis plan (SAP) will give more detailed descriptions of the endpoints in the study and the corresponding analyses.

2. Study Design

The protocol of this prospective, 2-arm, randomized controlled clinical trial and consent forms for the patients will be approved by the ministry of health and ethics committee of the university. The study will be registered on www.clinicaltrials.gov. The study will be following the Consolidated Standards of Reporting Trials (CONSORT) guidelines (**Moher et al. 2010**). All patients will be informed about the nature of the study, the treatment procedures, evaluation process, benefits, and the potential risks before they will be asked to sign a written consent form. The enrolment of patients will be executed from the outpatient clinic of Department of Endodontics, Faculty of Dentistry, Istanbul Medipol University, Turkey.

